14.1.2 Adverse Events of Special Interest

Occurrences of AEOsIs are derived based on the search strategy below. AEOsIs will be summarized in a similar manner to general adverse events for any and each AEOsI and listed as well. Only summaries involving Part 2 subjects are examined.

In addition, the exposure-adjusted incidence rate for each AEOsI will be summarized. This rate will be calculated as the number of individuals with the event starting at first study drug administration, divided by the total number of patient-years at risk for the event, multiplied by 100. In calculating patient-years at risk for a given event, the follow-up time for a patient experiencing that event will conclude at the event start date. If the subject never experience the event, the subject will be censored at the discontinuation visit, death, or last follow-up visit, whichever is earlier. Mean cumulative function plots will also be produced for any AEOsI if the number of events for that specific AEOsI are sufficient.

The following adverse events are of interest:

TERM	STRATEGY
hypophenylalanenemia	MedDRA Preferred Terms(PTs): Phenylketonuria, Amino acid level decreased and Amino acid level abnormal
convulsions	Standardised MedDRA queries(SMQs): Convulsions
epigastric ulcer	Standardised MedDRA queries(SMQs): Gastrointestinal ulceration, Gastrointestinal perforation and Gastrointestinal haemorrhage
nephrotoxicity	Standardised MedDRA queries(SMQs) of Broad acute renal failure, Broad chronic kidney disease or MedDRA HLGT Term(s) of Nephropathies and Renal disorders (excl nephropathies)
behavioural changes	MedDRA HLGT Term(s): Behaviour and socialisation disturbances

	SAP PKU-015, Version 3.0	Page 28 of 31
---	--------------------------	---------------

TERM	STRATEGY
nephrolithiasis	MedDRA HLGT Term(s): Renal lithiasis
GERD	MedDRA Preferred Terms(PTs): Gastroesophageal reflux disease, Barrett’s esophagus, and Gastrointestinal nonspecific inflammation and dysfunctional disorders
Hypersensitivity Reactions	Standardized MedDRA Queries(SMQs): Broad Hypersensitivity reaction
Anaphylactic reaction - Broad Algorithmic anaphylactic reaction SMQ	Standardized MedDRA Queries(SMQs): Broad algorithmic anaphylactic reaction
New onset anxiety disorders	MedDRA HLGT Term(s): Anxiety disorders and symptoms
Worsening of psychiatric disorders	MedDRA System Organ Class (SOC): Psychiatric disorders
Drug-drug interaction	MedDRA PTs: Phenylketonuria and Neurotransmitter level altered

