3.3 Study Population

Individuals eligible to participate in this study must meet all of the following criteria:

- Parent(s) or guardian(s) willing and able to provide written, signed informed consent after the nature of the study has been explained, and prior to any research-related procedures.
- Parent(s) or guardian(s) willing and able to comply with all study procedures.
- Female subjects of childbearing potential (as determined by the investigator) and sexually mature male subjects willing to use a medically accepted method of contraception throughout the study. Female subjects of childbearing potential willing to undergo periodic pregnancy tests during the course of the study
- Established diagnosis of PKU with hyperphenylalaninemia (HPA) documented in the medical record by at least 2 blood Phe concentrations $\geq 360 \mu\text{mol/L}$ (6 mg/dL) taken at least 3 days apart
- Documented blood Phe control (defined by the standard used at each treatment center) prior to study enrollment, if applicable (eg, the subject is old enough for these data to be collected); blood Phe concentrations for subjects < 6 months old at Screening must be considered controlled and stable by the Investigator

	SAP PKU-015, Version 3.0	Page 9 of 31
---	--------------------------	--------------

- Willing to adhere to a prescribed Phe-restricted diet in order to maintain blood Phe concentrations within the recommended ranges established at the subject's study site
- Age 0 to 6 years, inclusive, at Screening

Individuals eligible to participate in Part 2: Neurocognitive Study must meet **all** of the following criteria:

- Completion of Week 4 visit in Part 1
- Responsive to Kuvan during Part 1, defined as a $\geq 30\%$ average reduction in blood Phe concentration calculated as the mean of the weekly percent change from baseline in blood Phe concentration at Weeks 1, 2, 3, and 4
- Bayley-III or IQ test score ≥ 80 when tested within 6 weeks of determination of Kuvan responsiveness in Kuvan-responsive subjects

Individuals who meet any of the following exclusion criteria will not be eligible to participate in the study:

- Has known hypersensitivity to Kuvan or its excipients
- Use of Kuvan or any investigational product or investigational medical device within 30 days prior to screening, or requirement for any investigational agent prior to completion of all scheduled study assessments

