4.4 Study Day Derivation

Study Day 1 is used as the reference date for the derivation of Study Day in data analyses and displays, and is defined as the first date study drug is administered in Part 1. Study Day is computed by subtracting the Study Day 1 date from the visit date and plus 1 if the visit date occurs on or after the first study drug administration date. Otherwise, Study Day will be the visit date minus the Study Day 1 date. There is no Study Day 0. For specific efficacy analyses, Study Day 1 may also be defined as the day of the first neurocognitive assessment.

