14 SAFETY EVALUATIONS

Safety will be assessed by examining the incidence, severity grade, and relationship to study drug of all treatment-emergent adverse events (TEAEs) reported during the study period. In addition, clinical laboratory results, vital signs, ECG, and physical exam will be assessed. No formal statistical testing will be performed for the safety analyses; only descriptive statistics will be provided. Safety summaries will be presented for the Safety population using both group presentations as described in Section 4.2 unless noted otherwise.

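### AEoSI summaries cover Part 2 subjects only, so a dosed child who never enters Part 2, even one whose AEoSI ended participation in Part 1, is in no AEoSI summary table and, by context, not in the exposure-adjusted rate

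*SAP*

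**What the plan says.** Section 14 of the SAP sets the default: "Safety summaries will be presented for the Safety population using both group presentations as described in Section 4.2 unless noted otherwise". Under Section 4.1 the Safety population is everyone in the full analysis set who received any study drug, so it includes children treated in Part 1 only. Section 4.2 offers an optional Part 1 safety grouping: Part 2 Enrolled, Part 2 Not Enrolled, and Overall.

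Section 14.1.2 departs from that default for AEoSIs. It says "AEOsIs will be summarized in a similar manner to general adverse events for any and each AEOsI and listed as well", and the next sentence is "Only summaries involving Part 2 subjects are examined".

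The paragraph after that adds an exposure-adjusted rate with this definition: "the number of individuals with the event starting at first study drug administration, divided by the total number of patient-years at risk". The result is scaled to 100 patient-years. No population is named. First dosing belongs to Part 1: Study Day 1 "is defined as the first date study drug is administered in Part 1" (Section 4.4).

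Section 3.3 gives three conditions for Part 2: "Completion of Week 4 visit in Part 1"; an average reduction in blood Phe of at least 30%; and a Bayley-III or IQ score of at least "80 when tested within 6 weeks of determination of Kuvan responsiveness in Kuvan-responsive subjects".

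**The concern.** All enrolled children receive study drug for 4 weeks before anyone can enter Part 2. The AEoSI summaries then keep only those who passed the entry conditions. The first condition is to have stayed in the study through Week 4, so an AEoSI that ends participation in Part 1 removes the child from the very table meant to show that event. Hypersensitivity and anaphylactic reaction are both on the AEoSI list, and both can occur early in treatment.

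The rate has a related weakness. Read in context as a Part 2 rate, it counts time from first dose, including Part 1 time that every counted child had to complete. It can include a Part 1 event in a child who went on to Part 2, but not one that ended participation. A reader who sees a rate from first dose would reasonably take it to cover everyone who was dosed.

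**Working it through.** **Who is left out.** Three kinds of dosed child never enter Part 2: one who stops before completing Week 4, one who does not respond, and one who scores below 80. Only the first can be left out because of the AEoSI itself. The other two are left out for reasons that the SAP does not link to AEoSIs, but any AEoSI they had is still in no AEoSI summary table.

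**What the general tables show instead.** The tables in Section 14.1.1 are organised by system organ class (SOC) and preferred term. Section 14.1.2 lists 12 AEoSIs:

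- Eight are defined by a standardised MedDRA query (SMQ) or a high level group term (HLGT): convulsions, epigastric ulcer, nephrotoxicity, behavioural changes, nephrolithiasis, hypersensitivity ("Standardized MedDRA Queries(SMQs): Broad Hypersensitivity reaction"), anaphylactic reaction, and new onset anxiety disorders.
- Four are defined by preferred terms or a whole SOC: hypophenylalaninemia, GERD, worsening of psychiatric disorders, and drug-drug interaction.

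The four can largely be read from the general tables. The eight groupings cannot.

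**Size of the effect on the rate (illustrative).** The SAP gives no count of Part 1-only children, no AEoSI counts and no total exposure. I assume:

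- patient-years in Part 2 subjects, T: 45 × 7 = 315 (the completion target in Section 3.2) to 80 × 7 = 560 (the upper enrolment figure in Section 3.4);
- Part 1-only children: 10 to 80, with 28 days each, so t = 10 × 28/365.25 = 0.77 to 80 × 28/365.25 = 6.13 patient-years.

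With k children having the event among Part 2 subjects, the Part 2 rate is 100k/T. If one further event occurred in a Part 1-only child, the all-dosed rate is 100(k+1)/(T+t). Time at risk lost after an event is ignored.

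| k in Part 2 subjects | Part 2 rate compared with all-dosed rate, one omitted event |
|---|---|
| 0 | 0 instead of 100/566.13 = 0.18 to 100/315.77 = 0.32 per 100 patient-years |
| 1 | 49.0% to 49.9% lower |
| 3 | 23.5% to 24.9% lower |
| 10 | 7.3% to 9.0% lower |

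If no event is omitted, the Part 2 rate is higher than the all-dosed rate by t/T: 0.77/560 = 0.14% to 6.13/315 = 1.95%. If all 80 children were followed for 70 days (Week 4 plus the 6-week testing window), t = 80 × 70/365.25 = 15.33 and t/T = 15.33/315 = 4.9%.

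The Part 1 time of each counted child is also small: 28/(7 × 365.25) = 1.1% of a 7-year follow-up. The missing numerator matters, not the person-time.

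**Why a pooled percentage is not the repair.** Part 1-only children would enter its denominator with about 4 weeks of exposure. Take 60 Part 2 subjects with 3 events and one omitted event. The Part 2 figure is 3/60 = 5.0%. The pooled figure is 4/70 = 5.7% with 10 Part 1-only children, but 4/140 = 2.9% with 80. Pooling can therefore lower the percentage even while it adds an event.

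**The case against.** The strongest reply is that nothing here is wrong. Section 14 provides for exceptions, and Section 14.1.2 makes one. A Part 2 focus fits the stated scope of this SAP (Section 3) and the long-term safety objective (Section 3.1). That stands: a reader might infer a contradiction between Sections 14 and 14.1.2, and the text does not support it.

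A reader might also infer that these events go unreported. They do not. They remain in the Safety-population tables of treatment-emergent, serious and related events and of withdrawals and drug discontinuations, and in the adverse event listings. The restriction in Section 14.1.2 speaks of summaries, so the AEoSI listing is not clearly limited to Part 2. As written, it could show individual SMQ or HLGT cases from Part 1-only children. What is missing is their place in the grouped AEoSI tables and, by context, in the rate.

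Nor is it fair to call the rate's population undefined. The paragraph follows directly on the Part 2 restriction, so Part 2 subjects is the natural reading. If the restriction did not reach it, the Section 14 default would apply, the rate would cover all dosed children, and the omission from the rate would disappear. The tables and the rate beside them would then cover different children without a label. An explicit label is worth asking for on either reading.

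Finally, a deficit of about half is only what leaving out one of two events must produce. It is not evidence that the planned rate is wrong by that much, and a Part 2 rate is correct as a description of Part 2 subjects.

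**Conclusion.** The point holds as a minor one. As written, AEoSIs in dosed children who never enter Part 2 are in no AEoSI summary table, and one route to that exclusion is the AEoSI itself. By context the from-first-dose rate shares the restriction. No size can be derived from the SAP; the figures above rest on assumed exposure and assumed numbers of Part 1-only children. Under those assumptions the rate changes by about 2% or less if no such event occurs (4.9% in the 70-day case), and materially only if a rare AEoSI occurs early in a child who then leaves. Section 14 makes the safety analysis descriptive, and no decision rule uses the AEoSI rate.

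**What to change.** Keep the Part 2 AEoSI tables and label them as such. Replace the restricting sentence in Section 14.1.2 with wording such as:

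*AEoSI incidence tables are presented for Part 2 subjects and labelled accordingly. In addition, AEoSIs with onset during Part 1 are tabulated for the Safety population by Part 2 Enrolled, Part 2 Not Enrolled and Overall (Section 4.2).*

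Add to the rate paragraph:

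*The exposure-adjusted rate is calculated from first study drug administration for the Safety population and, beside it, for Part 2 subjects. Each rate is labelled with its population.*

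The label should say whether Part 2 subjects means all who entered Part 2 or the narrower Enrolled population of Section 4.1. The Safety-population rate also picks up an event after Week 4 in a responder who then fails the score criterion.

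Do not replace the Part 2 tables with a pooled percentage. Do not start a rate at Part 2 entry: the SAP defines no such date, and that origin would drop Part 1 first events in Part 2 children.

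The cost is SAP wording and one or two extra descriptive tables from adverse events already collected and coded, using groups that Section 4.2 already contains. The downside is an all-dosed rate that mixes short and long exposure, which is why the Part 1 table and the Part 2 rate should stand beside it.

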3.2 Study Design

This 2-part, multicenter, open-label study is designed to evaluate the safety of Kuvan and its effect on neurocognitive function, blood Phe concentration, and growth in children with PKU when treatment is initiated at 0-6 years of age. The study will be considered complete when approximately 45 subjects have completed 7 years of treatment.

One of the goals of the study will be to decrease blood Phe levels to reach a goal of ≤ 240 $\mu\text{mol/L}$. Subjects will meet with a dietician at each study visit to review dietary Phe intake. Dietary Phe may be added to the diet, at the discretion of the Investigator, if a blood Phe level falls below 120 $\mu\text{mol/L}$ or decreased if blood Phe level is above 240 $\mu\text{mol/L}$. If a subject's blood Phe falls below 120 $\mu\text{mol/L}$, at the discretion of the investigator, a gradual increase of approximately 5-20 mg/kg of Phe supplement may be added to the diet. If a subject's blood Phe level goes above 240 $\mu\text{mol/L}$, dietary Phe may be decreased by

	SAP PKU-015, Version 3.0	Page 7 of 31
---	--------------------------	--------------

approximately 5 to 20 mg/kg or defined by the standard used at each treatment center, at the discretion of the investigator.

Part 1: Evaluation of Kuvan Responsiveness

Beginning at Week 0 and after all baseline assessments are completed, subjects enrolled into the study will receive 20 mg/kg Kuvan daily for 4 weeks. Subjects will return to the clinic weekly for safety assessments and blood Phe concentration measurement. Subjects should continue with their current amount of dietary Phe intake. However, if a subject's blood Phe concentration drops below 120 $\mu\text{mol/L}$, at the discretion of the Investigator, a gradual increase by approximately 5 to 20 mg/kg of daily dietary Phe supplement may be added to the diet. It is important to avoid unstable swings in blood Phe concentrations. No dose adjustments can be made during Part 1 without consultation with the Medical Monitor.

Part 2: Neurocognitive Study

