Subjects who are responsive to Kuvan will continue to receive once a day doses of 20 mg/kg Kuvan orally. A Kuvan-responsive subject is defined as a subject with $\geq 30\%$ average reduction in blood Phe concentration calculated by the mean of the weekly percent change from baseline in blood Phe concentration at Weeks 1, 2, 3 and 4. The baseline blood Phe concentration is calculated as the mean of the results from Screening visit and at Week 0 (prior to dosing with Kuvan). At the discretion of the Investigator, the subject's daily Phe intake may be modified if blood Phe concentration falls below 120 $\mu\text{mol/L}$ during the study. Kuvan dose may also be reduced after Week 5 after consultation with the Medical Monitor, in subjects who do not tolerate the 20 mg/kg/day dose.

Neurocognitive testing will be performed within 6 weeks of determination of Kuvan responsiveness in all Kuvan-responsive subjects. The types of neurocognitive tests used (Bayley Scales of Infant and Toddler Development®-Third Edition [Bayley-III], Wechsler Preschool and Primary Scale of Intelligence™-Third Edition [WPPSI-III], and/or Wechsler Intelligence Scale for Children®-Fourth Edition [WISC-IV]) will be those appropriate for the subject's current age at assessment. Table 3.2.1 shows the neurocognitive test to be used according to subject age.

	SAP PKU-015, Version 3.0	Page 8 of 31
---	--------------------------	--------------

Table 3.2.1: Neurocognitive Assessments

Age Group	Infancy	Preschool		School-Age
Assessment	Bayley-III	WPPSI-III (First Form)	WPPSI-III (Second Form)	WISC-IV
Age	0 months through < 30 months	30 months through < 4 years	≥ 4 years through < 7 years	≥ 7 years and older
Frequency	Every 6 months ± 2 weeks	Once a year ± 2 weeks	Once a year ± 2 weeks	Every 2 years ± 2 weeks

Growth, blood Phe concentration, and safety will be monitored. These and the neurocognitive assessments will be performed every 6 to 24 months, depending on the type of assessment, until the end of the study.

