	Month 24	Day 549 to Day 913
	Month 12*i, where i=2,3,4,5,6,7,...	Day $365*i - 181$, Day $365*i + 183$
	Blood Phe level, Dietary Phe, Weight, Vital Signs	Baseline
Week 1		Day 2 to Day 11
Week 2		Day 12 to Day 18
Week 3		Day 19 to Day 25
Week 4		Day 26 to Day 42
Month 2		First measurement date after determination of Kuvan responsiveness (Day 43 to Day 76)
Month 3		Day 77 to Day 106
Month 4		Day 107 to Day 137
Month 5		Day 138 to Day 167
Month 6		Day 168 to Day 273

	SAP PKU-015, Version 3.0	Page 15 of 31
---	--------------------------	---------------

Assessment	Scheduled Time Point	Visit Window
	Month 12	Day 274 to Day 456
	Month 18	Day 457 to Day 638
	Month 6*i, where i=2,3,4,5,6,7,...	Day $\text{round}(182*i + i/2) - 91$, Day $\text{round}(182*i + i/2) + 91 - \text{mod}(i,2)^*$
Additional Week 0 Vital signs	15 min postdose	1 min to 22 min elapsed time
	30 min postdose	23 min to 37 min elapsed time
	45 min postdose	38 min to 52 min elapsed time
	60 min postdose	53 min to 75 min elapsed time
	90 min postdose	76 min to 105 min elapsed time
	120 min postdose	106 min to 150 min elapsed time
	180 min postdose	151 min to 360 min elapsed time
Clinical laboratory tests	Baseline	Last measurement date prior to the initial study drug administration
	Week 1	Day 2 to Day 15
	Week 3	Day 16 to Day 25
	Week 4	Day 26 to Day 42
	Month 2	First measurement date after determination of Kuvan responsiveness (Day 43 to Day 76)
	Month 3	Day 77 to Day 106
	Month 4	Day 107 to Day 137
	Month 5	Day 138 to Day 167
	Month 6	Day 168 to Day 273
	Month 12	Day 274 to Day 456
	Month 18	Day 457 to Day 638
	Month 6*i, where i=2,3,4,5,6,7,...	Day $\text{round}(182*i + i/2) - 91$, Day $\text{round}(182*i + i/2) + 91 - \text{mod}(i,2)^*$

*Baseline refers to first assessment for this visit windowing

	SAP PKU-015, Version 3.0	Page 16 of 31
---	--------------------------	---------------

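### For adverse events of special interest found mainly by a blood test, one rate and one cumulative curve span three testing frequencies, so the curve can flatten because testing thins out

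*SAP*

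**What the plan says.** **Event summaries (SAP 14.1.2).** AEoSIs are found by MedDRA searches of reported adverse events and summarised for Part 2 subjects. The exposure-adjusted rate is the number of children with the event from first dose, "divided by the total number of patient-years at risk for the event, multiplied by 100". A child's time at risk ends at the first event or at censoring. On the time course, the SAP says "Mean cumulative function plots will also be produced for any" AEoSI with enough events. It sets no split by period and makes no reference to testing frequency.

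**Testing (SAP 3.2 and 4.5).** In Part 1, "Subjects will return to the clinic weekly for safety assessments and blood Phe concentration measurement". Table 4.5.1 then lists blood Phe at Months 2, 3, 4, 5 and 6 (the Month 6 window is "Day 168 to Day 273"), and from there at "Month 6*i, where i=2,3,4,5,6,7" and so on. Section 3.2 agrees that later monitoring is "performed every 6 to 24 months, depending on the type of assessment". Clinical laboratory tests thin out in a similar way: Weeks 1, 3 and 4 and Months 2 to 6 make 8 time points, followed by one every 6 months.

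**Search terms.** Hypophenylalaninaemia is identified by three preferred terms, two of which (*Amino acid level decreased*, *Amino acid level abnormal*) are laboratory findings.

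**The concern.** A low blood Phe value is unlikely to be reported as an adverse event unless blood was drawn. If the number of draws per year falls sharply, the number of reported events per year can fall with it while the child's risk stays the same.

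Two displays are exposed, in different ways. The mean cumulative function (MCF) has a time axis, so its slope can drop at each thinning of the schedule. The pooled first-event rate has no time axis; it averages person-time under very different testing intensities, so its value depends on how long children were followed. Follow-up will vary: 60 to 80 responders are to be enrolled (3.4), and the study closes when about 45 have completed 7 years (3.2).

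Long-term safety is the first secondary objective (3.1), and with no control arm there is no comparator tested on the same schedule to expose the artefact. A flattening curve for low Phe invites the reading that the risk wears off with time on drug.

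**Working it through.** The SAP states no figure on this point, so there is none to reproduce. Table 4.5.1 supplies the test counts. The event probability and the episode length are assumptions.

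**1. Count the scheduled post-baseline Phe tests to Year 7.**
- First dose to Week 4: 4 tests in 4 weeks, or 4 / (4/52) = 52 per year.
- Week 4 to Month 6: 5 tests in about 154 days, or 5 / (154/365) = about 12 per year.
- After Month 6: 2 per year (Months 12, 18, …, 84 = 13 tests).
- The first half-year together: 9 / 0.5 = 18 per year, against 2 afterwards, a ratio of 9. It holds 9/22 = 41% of the tests in 0.5/7 = 7% of the follow-up.

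**2. Constant probability p per scheduled test (assumed).** MCF slope = p × tests per year. At p = 1% that is 18 per 100 patient-years before Month 6 and 2 after. The ratio of 9 does not depend on p.

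First-event rate = 100 × expected first events / expected years at risk, at p = 1%:

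| Period or follow-up | Rate per 100 patient-years |
|---|---|
| First dose to Week 4 | 50.4 |
| Week 4 to Month 6 | 11.9 |
| After Month 6 | 2.0 |
| Pooled, everyone followed 6 months | 18.2 |
| Pooled, 3 years | 4.8 |
| Pooled, 7 years | 3.3 |

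Risk per test is the same in every row. At p = 5%, the pooled 6-month and 7-year figures are 96.1 and 19.6.

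**3. Constant true episode rate, episode length D days (assumed).** Step 2 supposes that the chance of a finding does not depend on the gap since the last test, which suits short episodes only. Suppose instead that an episode is found only if a scheduled test falls inside it. The fraction of episodes found in a period is then the sum of min(D, gap before each test), divided by the length of the period. With tests on days 8, 15, 22, 29, 61, 91, 122, 152 and 183, the gaps are 8, 7, 7, 7, 32, 30, 31, 30 and 31 days; later gaps are about 182.5 days.

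| D (days) | Found before Month 6 | Found after Month 6 | Ratio |
|---|---|---|---|
| 7 | 63/183 = 0.344 | 7/182.5 = 0.038 | 9.0 |
| 14 | 99/183 = 0.541 | 14/182.5 = 0.077 | 7.1 |
| 30 | 179/183 = 0.978 | 30/182.5 = 0.164 | 6.0 |
| 90 | 183/183 = 1 | 90/182.5 = 0.493 | 2.0 |
| 183 or longer | 1 | 1 | 1.0 |

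A separate simulation gave about 9.0, 7.0, 5.9, 2.0 and 1.0.

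**4. Would events per test solve it?** No. For episodes of 183 days or longer, all are found in both periods, yet each early test carries on average 183/9 = 20.3 days' worth of episodes and each late test 182.5. Events per test would rise 182.5/20.3 = 9-fold at constant risk, which is the opposite artefact.

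**The case against.** - **Table 4.5.1 gives analysis windows, not a cap on testing.** Section 4.5 provides for more than one measurement in a window, and the Index of Dietary Control in 13.3.2 uses half-year medians, which would have little point with one value per half-year. The test schedule itself belongs to the protocol. This stands: actual sampling after Month 6 may be denser, and the contrast smaller. It does not remove the point, because 3.2 puts later Phe monitoring at 6 months or longer and the SAP describes no other routine tests.
- **The effect needs short episodes.** This also stands. A persistent renal abnormality would still be there at a 6-monthly test, giving a ratio near 1.
- **Few AEoSIs are affected.** Correct. Of the 12 listed, only hypophenylalaninaemia clearly rests on Phe testing. Nephrotoxicity is searched with broad renal queries, and nothing says that its cases come mainly from laboratory results.
- **A split does not separate detection from a real early effect** when drug starts and diet may change. True; what it does is stop the two from being read as one trend.
- **Safety is descriptive (section 14), listings are planned, and the MCF is drawn only if events suffice.** This limits the stakes. But without a control arm, these displays are the safety evidence.

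A reader might infer that detected events must fall with time on drug by construction, or that the pooled rate itself shows a decline. The documents support neither. The first needs short episodes and no denser testing, and a single pooled number has no time axis.

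**Conclusion.** The concern holds for AEoSIs found mainly by a blood test: chiefly hypophenylalaninaemia, and possibly laboratory-based renal terms. For these, the MCF can flatten because testing thins, and the pooled first-event rate blends detection intensities and depends on length of follow-up.

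The distortion between the first 6 months and later ranges from none (episodes of about 6 months or longer) to about 9-fold (episodes of days), and is less if unscheduled tests are common. That range assumes constant true risk, complete attendance and detection only at the time points in Table 4.5.1. The rates per 100 patient-years also assume a per-test probability that the SAP does not give, and serve only as illustration. No formal test is affected. The consequence is a possible misreading of the long-term safety displays, which a modest change would prevent.

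**What to change.** In SAP 14.1.2, for hypophenylalaninaemia and any other AEoSI judged to be found mainly by laboratory testing:

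- Report the exposure-adjusted rate separately for first dose to Week 4, Week 4 to Month 6, and after Month 6 (children still at risk), beside the pooled rate. A single cut at Month 6 is not enough, because testing already falls from about 52 to about 12 per year at Week 4. Define the cuts so that findings at the Week 4 and Month 6 visits fall in the period that each visit closes.
- Give the number of Phe tests actually done in each period, unscheduled ones included where recorded. This shows how far testing really thinned.
- Mark both schedule changes on the MCF plot, and state that a change in slope across them is not evidence of a change in risk.
- Do not use events per 100 tests as the main measure, given the reverse artefact for long episodes.

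The cost is SAP wording, a few table rows and a figure annotation, with no new data collection. The downside is fewer events, and so wider uncertainty, in each period.

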14.1 Adverse Events

14.1.1 All Adverse Events

Adverse events will be coded in accordance with the most current version of MedDRA at program termination or annual reporting. Only treatment-emergent adverse events (TEAEs) occurring and reported during the study will be included in the adverse event summaries. A TEAE is defined as any AE that newly appeared or worsened in severity following initiation of the study drug administration. If the onset date of an AE is missing, the AE will be considered treatment-emergent. The incidence of all treatment-emergent AEs will be summarized by system organ class (SOC), preferred term (PT), relationship to study drug and CTCAE grades. For those AEs that occurred more than once, regardless of study part, the maximum severity will be used to summarize the AEs by severity.

If the onset date or end date of an adverse event is partial, the same imputation rules described in section 9 will be applied.

The treatment-emergent AEs will be summarized in the following categories:

- All AEs by SOC and preferred term
- All AEs by preferred term in descending frequency order
- All AEs by SOC, preferred term, and NCI CTCAE grade
- AEs assessed by investigators as related to study drug by SOC and preferred term
- AEs assessed by investigators as related to study drug by SOC, preferred term and NCI CTCAE grade
- Serious AEs (SAEs) by SOC and preferred term
- All SAEs by preferred term in descending frequency order

	SAP PKU-015, Version 3.0	Page 27 of 31
---	--------------------------	---------------

- SAEs assessed by investigators as related to study drug by SOC and preferred term
- Death
- AEs leading to withdrawal from study by SOC and preferred term
- AEs leading to study drug discontinuation by SOC and preferred term

A summary of all AEs and adverse event listings will also be provided.

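### The hypophenylalaninaemia search includes the disease term Phenylketonuria and a direction-free term, and Phenylketonuria is also searched as a drug-drug interaction, so both event rates could be inflated

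*SAP*

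**What the plan says.** SAP section 14.1.2 makes the term search the rule for finding cases: "Occurrences of AEOsIs are derived based on the search strategy below". The hypophenylalaninaemia row reads "MedDRA Preferred Terms(PTs): Phenylketonuria, Amino acid level decreased and Amino acid level abnormal". The drug-drug interaction row reads "MedDRA PTs: Phenylketonuria and Neurotransmitter level altered". The section states no direction check, blood Phe value, case review or rule for a term that sits in two rows.

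The same section says that "the exposure-adjusted incidence rate for each AEOsI will be summarized", as subjects with the event per 100 patient-years at risk. On time at risk, "the follow-up time for a patient experiencing that event will conclude at the event start date". Mean cumulative function plots follow where there are enough events. These summaries cover Part 2 subjects.

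Two other places fix the meaning of the disease term. Entry under section 3.3 requires "Established diagnosis of PKU with hyperphenylalaninemia (HPA) documented in the medical record by at least 2 blood Phe concentrations" of at least 360 µmol/L. Section 14.1.1 covers existing disease that gets worse: "A TEAE is defined as any AE that newly appeared or worsened in severity following initiation of the study drug administration".

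**The concern.** The row is labelled as low Phe, but one of its terms names a disease that the SAP documents by high Phe, and another says only that an amino acid level was abnormal. Every subject has PKU. If an investigator reports worsening PKU and it is coded to Phenylketonuria, the search returns it as hypophenylalaninaemia. The same report is also returned as a drug-drug interaction, whether or not any other medication was involved.

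Low Phe is a natural safety question for a drug that lowers Phe. A rate that mixes it with events in the opposite direction does not answer that question. An interaction rate fed by the disease term has the same fault.

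**Working it through.** The plan states no event rate for these events, so there is no figure to reproduce. The check has two parts.

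**1. The two term lists side by side (SAP section 14.1.2)**

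| Preferred term | States a decrease? | Low-Phe row | Interaction row |
|---|---|---|---|
| Phenylketonuria | No; disease documented by high Phe (section 3.3) | Yes | Yes |
| Amino acid level decreased | Yes | Yes | No |
| Amino acid level abnormal | No; no direction | Yes | No |
| Neurotransmitter level altered | Not relevant | No | Yes |

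One of the three low-Phe terms carries the direction that the label claims. Phenylketonuria is the only term in both rows.

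The written rules then run as follows. A worsening of PKU reported as an adverse event is treatment-emergent (section 14.1.1). If it is coded to Phenylketonuria, the search captures it in both rows (section 14.1.2). The subject enters both numerators, and time at risk stops in both denominators. If the same subject later has a true low-Phe event, the numerator does not change, but follow-up has already been cut at the wrong event.

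**2. Illustration of the effect on the rate**

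Inputs from the SAP: 60 to 80 responsive subjects (section 3.4) and 7 years of treatment (section 3.2). Assumed inputs: every subject is followed for 7 years unless an event occurs, events fall at mid follow-up (3.5 years), 3 subjects have true low-Phe events, and H further subjects have a high-Phe event coded to Phenylketonuria.

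With k subjects counted as having the event among N:

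rate = 100 × k / [7 × (N − k) + 3.5 × k]

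For N = 60:
- True low-Phe rate, k = 3: 300 / (399 + 10.5) = 0.73 per 100 patient-years.
- H = 3, k = 6: 600 / (378 + 21) = 1.50.
- H = 6, k = 9: 900 / (357 + 31.5) = 2.32.
- H = 12, k = 15: 1500 / (315 + 52.5) = 4.08.

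The H subjects alone give a drug-drug interaction rate of 0.73, 1.50 or 3.17 (k = 3, 6, 12), with no interaction having been reported.

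For N = 80 the true low-Phe rate is 0.55, and the reported rate is 1.11, 1.70 or 2.96. The interaction rate is 0.55, 1.11 or 2.32.

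With H = 0 there is no distortion. The documents do not say which H is realistic.

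**The case against.** **Broad and overlapping searches run through the whole table.** Several rows use broad standardised queries, and the whole psychiatric system organ class sits beside a separate anxiety row. An event under two headings is therefore not in itself an error, and the section 15 change log suggests that the list follows periodic safety reports and a risk management plan that are not shown. This stands as a reason to keep the present search in some form. It does not explain why a search for low Phe should contain the term for the opposite state. The low-Phe row is not labelled broad, and no reason is given.

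**Other outputs let a reader separate the terms.** Adverse events are tabulated by preferred term (section 14.1.1), and events of special interest are summarised in a similar way and listed. This stands in part. It does not reach the pooled rate or the plots, and direction cannot be recovered from Amino acid level abnormal. Section 13.3.2 gives the proportion of Phe values between 120 and 360, which does not separate low from high. The low/normal/high shift tables in section 14.2 do not name Phe.

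**The consequence is limited.** Safety is descriptive with no formal testing (section 14), and the FSIQ analysis is untouched. This stands.

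**Four stronger readings are tempting, but the documents do not support them.**
- That high-Phe events will in fact be reported as low Phe. This depends on coding that the SAP does not describe; a high-Phe event coded outside these terms is not captured.
- That every subject would count, since all have PKU. The treatment-emergent rule requires a new or worsened event.
- That both non-specific terms are counted twice. Only Phenylketonuria is in both rows.
- That most captured events would be high-Phe events. Any such ratio rests on an invented Phe distribution and a chosen cut-off. For Phe distributed N(240, 100), the ratio of values above 240 to values below 120 is 0.50 / 0.115 = 4.3; with 360 as the upper limit it is 0.115 / 0.115 = 1. For N(300, 100) the ratios are about 20 and 7.6. Measured values are also not reported adverse events.

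**Conclusion.** The concern holds as a flaw in the written search rule. The low-Phe search admits a term tied to high Phe and a term without direction, and Phenylketonuria also feeds the interaction search. The exposure-adjusted rates and any mean cumulative function plots for these two events could be inflated, and they would not mean what their labels say.

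The amount cannot be stated. It depends on how many treatment-emergent events that are not low Phe, or not interactions, are coded to these terms. The figures in the illustration show how the rate responds to assumed counts and are not estimates. The point concerns safety reporting only, but it merits correction because the rule is wrong on its face and cheap to mend.

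**What to change.** 1. Base the hypophenylalaninaemia rate and plot on terms that state a decrease. Count Phenylketonuria or Amino acid level abnormal only when the verbatim term or a concurrent blood Phe result shows low Phe.
2. Remove Phenylketonuria from the drug-drug interaction search unless the report names an interacting medication.
3. Keep the existing search as a secondary table, so that counts can still be compared with periodic reports.
4. If wanted, summarise blood Phe below 120 µmol/L separately as a descriptive laboratory result. It should not define the event of special interest, because in the SAP (section 3.2) 120 is a level for discretionary diet changes. It could also flag most subjects. The section 4.5 windows give about 22 post-baseline Phe time points through Year 7 (Weeks 1 to 4, Months 2 to 5, then every 6 months from Month 6 to Month 84: 4 + 4 + 14). Assuming independent values, the share of subjects with at least one value below 120 is 1 − 0.885^22 = 93% under N(240, 100) and 1 − 0.964^22 = about 55% under N(300, 100).

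The cost is a change of SAP wording, a short review of verbatim terms against blood Phe already collected, and some difference from counts in earlier reports, which the secondary table makes traceable.
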